Useful Field of View. *This task will measure brain changes due to alterations in attention and decision-making processes due to BrainHQ Double Decision and Freeze Frame training.* We will assess attentional and decision-making processes on a scanner adapted event related UFOV task that requires participants to simultaneously apprehend the identification of a centrally located target (car or truck) and the location of a target (car) among a parametrically manipulated array of distractors (0-47 distractors). Following a visual mask, participants then make a two-alternative forced choice (correct or incorrect) decision based on whether both the central target and distal target (without distractors) are identical to what was seen in the prior display (Figure 17). Two five-minute blocks of 56 trials are presented. Accuracy and reaction times are recorded. Jitter prior to stimulus presentation and response probe allows contrasts assessing unique activation associated with attentional and decision-making brain regions, providing mechanistic insight into cognitive training effects.

Figure 17. Useful Field of View (UFOV) Task

Resting State. Participants will also be asked to rest for 6 minutes while functional data is being collected to assess resting state activation.

6.6.2. Proton Magnetic Resonance Spectroscopy (MRS): GABA-edited spectra will be acquired using the MEGA-PRESS experiment, from a 3x3x3 cm³ voxels (medial frontal). Spectra will be analyzed using Gannet and LCModel to assess cerebral metabolites and neurotransmitter concentrations.^{295, 412,413}

6.6.3. Structural MRI. High-resolution whole brain axial gradient-echo MPRAGE 3-D T1-weighted images will be acquired for volumetric and cortical thickness analyses and fMRI localization. Analyses: Volumetric indices will be obtained for total gray and white matter, FreeSurfer ROIs²⁹⁶⁻²⁹⁸, and a priori ROIs (MRS, fMRI).

6.7. Neurocognitive Assessment: Assessments will include a neurocognitive battery (see Table 7). The battery consists of standardized, well-established neurocognitive measures with strong reliability and validity³⁰⁴. For cognitive measures with functions assessed see Table 7 below. Our goal is to assess global cognitive ability (NIH-Toolbox: cognitive module), and specifically attention-executive functions, working memory, processing speed, and memory. These are domains affected by aging^{24,31,146,305-314} and will also tap the domains assessed by fMRI (Aim 2).

Table 7. Neurocognitive Assessment	
HVLT	Verbal Learning/Memory
Stroop	Attention/Executive
Trail Making A & B	Executive
COWA & Animals	Verbal Fluency
BVMT	Visual Memory
Symbol Digit Coding	Processing Speed
Letter Number Sequencing	Working Memory
PASAT	Working Memory
Digit Span	Working Memory
NIH Toolbox Subtests:	
* Dimensional Card Sort	Executive
* Flanker	Attention/Executive
* Picture Sequence	Episodic Memory
* Picture Vocabulary	Language
* Oral Reading	Language
* Pattern Comparison	Processing Speed
* List Sorting	Working Memory

6.7.1. Functional Outcomes. A touchscreen computer-based functional assessment tool will be used to measure tasks like medication management, ATM banking, prescription refill via voice menu. Task difficulty can be varied and real-time efficiency and accuracy data are collected; the measure is highly correlated with component cognitive abilities targeted in this study^{315,316}. See Appendix 2 for a detailed manual.

6.7.2. QOL and PROMIS self-reported health assessment. We will administer *the Medical Outcomes Study Short Form-36 (SF-36: v. 2.0*, a widely used QOL measure), and the PROMIS self report measures at each assessment. The PROMIS measures assess change in self-reported cognitive and physical function.^{321 321} Change in self reported physical and mental health status correlate with QOL and mental and physical health status.^{322,323 324} These two measures will serve as important assessments of interventions influence on everyday life.

6.8. Alcohol and Drug Use Questionnaires. We will administer the Alcohol Use Disorders Test (AUDIT-10) and Drug Abuse Screening Test (DAST-10). These measures will provide

valuable information about how drug and alcohol use may alter the overall efficacy to tDCS, cognitive training and education training.

6.9. Driving Record Assessment. Driving records will be requested following the completion of the intervention; records will be requested at 5 years post intervention and at 10 years post intervention. These records will allow us to examine real world driving outcomes. The driving record assessment is optional (the participant chooses to consent to this portion or not at screening). Participants who do not consent to the driving record assessment can still participate in the study.

6.10. Walking assessment. We will administer a 10-meter walk test. This test measures the time it takes participants to walk ten meters in a line. Participants are instructed to walk at their normal pace, as if they were walking down the street. Participants are instructed to use any walking aids they normally use (e.g. cane).

6.11. Quality Control. We will record (with audio and/or video) study procedures for the purpose of ensuring quality data collection. Participants will consent (via a checkbox on the informed consent form) to this recording. Recording will only be done on participants who provide written consent.

6.12. Theft Prevention. This study will be loaning out university computers and other supplies. All university equipment must be returned when the participant completes or withdraws from the study. In the event university equipment is stolen we will be required to file a police report with local authorities. We will make copies of the participant's driver's license when they are provided university equipment. Having a copy of the driver's license provides us with needed information in the event of lost or stolen university property. This procedure is described in the informed consent form. As a driver's license is protected health information it will be kept separate from any de-identified data.

6.13. Transportation. Certain potential participants may lack reliable transportation to the study sites. When possible study staff may transport willing participants to the study sites using a vehicle owned by the Department of Clinical and Health Psychology. All study staff will follow the procedures and regulations for operating University owned vehicles as described by UF Environmental Health and Safety at: <http://www.ehs.ufl.edu/programs/insurance/automobile/>

To facilitate transportation to and from the study site Uber Health may be used if the participants desire to have transportation provided. All costs associated with Uber Health will be covered by the study; the participant will not have any cost associated with the Uber Health travel. The option to have travel provided will be offered to all potential study participants within a 40 mile radius of the study site as costs outside of a 40 mile radius will not be feasible with the current travel budget.

Uber Health offers a HIPAA compliant service designed specifically with enhanced ease and privacy in mind for those using the service. Participants will not need to have any account associated with Uber and study staff will coordinate the whole process. The Uber driver will send the participant a text when they are about to arrive at their location, however, the participants personal phone number will not be revealed and instead a covert masking of numbers is provided by Uber to allow the driver and passenger to communicate without revealing their personal phone numbers. If participants do not have or use mobile phones the study coordinator can help coordinate the pickup.

6.14. Payment. Participants will receive \$75 in gift cards at the end of each of the three MRI sessions to compensate them for their time and effort.

If participants are traveling from more than 20 miles away (one-way) to the study location they will receive an additional \$10 compensation per study visit. If they attend all study visits they will receive an additional \$270 in compensation for travel. If participants live less than 20 miles away they will receive no additional compensation for travel. If participants are utilizing Uber Health for transportation they will not receive the additional \$10 per visit compensation.

6.15. Notification of Participants for Cognitive Findings Leading to Study Exclusion. The Montreal Cognitive Assessment (MoCA) serves as a brief global dementia screening tool commonly implemented in clinical practice. Any participant falling below the 1.5 SD norms (adjusted for age and education) would screen fail in the ACT study, as per current criteria. If this occurs, the participant will first be contacted via phone call by the study physician ([name]) and then provided with a letter from the study team describing their reason for screen fail and encouraging them to follow up with their primary care physician (the letter and phone call template are submitted in miscellaneous attachments in the myIRB system). The procedure for implementation will be built into our RedCap data system such that any person meeting this criterion will trigger an email to the site PI and site physician alerting the team to follow up with the participant and to provide the phone call by the study physician and a letter notifying the participant.

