GABA, the brain’s principle inhibitory neurotransmitter,²¹² is essential for synaptic communication and regulation of neuronal excitability,²¹³ and neural plasticity.²¹⁴⁻²¹⁸ It plays a key role in learning and memory²¹⁹⁻²³⁵ and modulates other behavioral and affective functions, including executive control and attention.²³⁶⁻²³⁸ Decreased cerebral GABA occurs with advanced age,^{219,223,227,230} and GABA dysregulation occurs in neurological and psychiatric conditions.^{49,239-267} GABA delivered to the frontal cortex and hippocampus in animals facilitates cognitive and working memory performance. GABA can now be reliably measured using proton MRS,^{5,268-273} based on seminal work by [name] (consultant).²⁷⁴⁻²⁷⁸ GABA provides an in vivo biomarker of neural plasticity in brain ROIs important for the cognitive functions to be trained in our study.²⁷⁶

84

Figure 1

Summary and Conceptual Model. Age-associated functional, structural and metabolic brain changes occur, even in the absence of frank neurodegenerative disease. CT holds promise for reducing the adverse effects of cognitive aging, enhancing neural plasticity, cognitive efficiency, functional capacity, and quality of life. In theory, CT benefits could be augmented by coupling it with other interventions that either increase neural plasticity. Yet, relatively few of these approaches

have been tested in RCTs, and the mechanisms underlying their effects are largely unknown. Even less is known about the combined effects of CT with tDCS. Our preliminary data provides strong support for CT to combat cognitive aging, and also for the effects of tDCS on cognition and brain function. We hypothesize that CT leads to improvements in neural plasticity (GABA MRS) and functional brain response (fMRI). In turn, this can lead to improved cerebral metabolic health and structural brain preservation. Coupling CT with tDCS will increase neural plasticity in brain areas important for working memory, focused attention, and executive control, improve effectiveness of CT, and ultimately cognitive health (see Figure 1 for conceptual model).

5. Specific Aims:

Aim 1. Determine whether neurocognitive improvement and longer-term functional outcome (as measured by “ecological assessment”) are better when CT is coupled with tDCS, an intervention that will increase neuroplasticity and augment training effects.

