6.1. Experimental design. This study employs a two-phase randomized clinical trial with 360 participants total across two sites (University of Florida and University of Arizona; 240 at the University of Florida and 120 at the University of Arizona). UF will be the parent site for the study. An initial cohort of 80 participants collected across the two sites will be assigned to one of four conditions as shown in Figure 2. Half of the recruited sample in Phase 1 will undergo CT; the other half will undergo training control (TC). The first interim analysis, to be performed when the first cohort of 80 completes 12-month follow-up (Phase 1), will investigate whether CT is significantly better than TC thereby enabling elimination of the TC condition. CT has previously been established with strong effects on cognitive and functional outcomes. If CT and TC are equally effective, groups will be collapsed at initiation of Phase 2 for planned assessment of adjunctive tDCS effects. If CT is more effective than TC, as previously shown, TC will be eliminated. Data from Phase 1 will also provide important mechanistic insight regarding neural mechanisms of CT vs. a well-matched education training control (TC). In Phase 2, the remaining 280 participants will be randomized to the two CT arms (i.e., eliminating the TC arms). After the remaining 280 participants have completed follow up in the CT arms (including those in Phase 1, total n=360) analyses will investigate the benefit of adjunctive administration of CT with tDCS. **Participants will be assessed at three primary time points: 1) baseline pre-training; 2) post-12 weeks of CT/TC + stimulation/sham; and 3) one year follow-up after all training (see Figure 3 for timeline).** This design will enable longitudinal analyses of CT and tDCS effects individually and in combination. We will examine CT and tDCS effects on cognitive performance, functional and metabolic neuroimaging measures, and everyday functional abilities. At each assessment, we will obtain clinical and medical history, neurocognitive measures, and neuroimaging (structural MRI, fMRI, MRS). All participants will undergo neuroimaging at baseline, following CT, and at one-year follow-up.

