6.2. Study participants and randomization procedure. We will recruit 240 older adults (women = 120; age: 65-89 years) at UF. Study participants will consist of healthy individuals who have expressed an interest in taking part in an intervention aimed at optimizing and possibly preserving cognitive functioning and brain health. Web-based permuted block randomization (with block size 8) will be used. In phase 1, each block will have two participants for each arm. In phase 2, each block will have four participants for each remaining arm. We will enroll people with evidence of age-related cognitive decline as defined by performance below the 80th percentile on the Cognitive Training assessment. People with pre-existing dementia, neurological brain disease, or who meet criteria for a diagnosis of mild cognitive impairment (MCI) will be excluded.

[figure not shown]
6.2.1. Experimental Design Considerations and Limitations: CT Approach. The POSITScience BrainHQ treatment program was selected because it 1) provides specific training tasks directed at three essential cognitive domains tied to our aims and hypotheses (attention, working memory, executive control) that correspond with the neurocognitive and functional neuroimaging measures to be studied; 2) is shown to produce significant cognitive and functional improvements with good effect sizes in past RCTs (ACTIVE) with up to 10 year durability and transfer of training to measures of self-reported everyday functioning; 3) provides a “cognitive treatment engine²⁸²” which alone has a very highly likelihood of yielding significant cognitive and functional improvements, enabling us to test the augmenting effects of tDCS; and 4) is computerized, well standardized, and efficiently implemented.

Combined CT. We selected a combined CT approach rather than testing one specific training task: 1) This would optimize CT treatment effects for this primary intervention, providing a strong and reliable engine of change with which to examine effects of tDCS; 2) This approach enables us to affect several related cognitive functions that are strongly dependent on neural plasticity of the frontal cortex; and 3) This approach would maximize participants interest and motivation versus a single task that could become boring.

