Neuroimaging measures. We will focus on functional (fMRI) and cerebral metabolic (proton MRS) indices for two reasons: 1) These modalities are most linked to and likely sensitive to CT-associated neural plasticity and brain changes; and 2) Changes in these domains are likely to occur over the course of training compared to structural neuroimaging measures. We include active fMRI tasks related to the cognitive functions to be trained, as well as a passive resting state condition to examine the DMN. With respect to MRS, we use a single voxel method to achieve optimal sensitivity and will measure from a single ROI (frontal) corresponding to task and resting state associated brain areas. Along with Creatine (Cr), we will examine cerebral metabolites sensitive neuronal loss and membrane disturbances (NAA, GLx), and pro-inflammatory processes (Ch, MI). We will also measure cerebral GABA concentrations using a state of art MRS approach that will reflect neural plasticity in ROIs. The MRS indices will be examined for Aims 2.

6.3. Procedural sequence. The sequence and flow of the assessments to be conducted at baseline and each subsequent assessment is shown in Subject Timeline.

Single Subject Timeline	Month														
	0	1	2	3	4	5	6	7	8	9	10	11	12	13	14
Phone Screening															
Consent Form															
Screening															
Baseline Measurements															
Cognitive Training/tDCS															
Post-CT Measurements															
1 Year Follow-Up Measurements															

Study Timeline	Year 1			Year 2			Year 3			Year 4			Year 5			
	3	6	9	12	3	6	9	12	3	6	9	12	3	6	9	12
Project Start-Up																
Recruitment/Screening				C1*					C2							
Baseline Measurements				C1					C2							
Cognitive Training/tDCS				C1					C2							
Post-CT Measurements				C1					C2							
1 Year Follow-Up Measurements								C1							C2	
Interim Analysis (IA)								IA								
Final Data Analysis																

* Notes: 1) Number of participants in Cohort 1 and 2 are 80 and 280, respectively. The allocation ratio for the last cohort depends on results from IA. Measurements = MRI/Neurocog/Functional Outcomes

Screening Visit

Task	Estimated Time
Informed Consent	45
Full medical History/rx drugs	15
MRI screening form	5
NACC UDS	45

WTAR	5
BDI	5
Computer use questionnaire	5
Vision/color vision/hearing	10
AD-8	3
Cognitive Training assessment	20

Assessment Visits

Task	Estimated Time
MRI scan	60
MRI scan practice	20
MRI safety questionnaire	5
NIH toolbox	45

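### The rule that collapses training groups after Phase 1, and a final tDCS sample of 360 where the CT arms hold 320, leave the primary tDCS comparison averaging over two background trainings

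*Combined protocol and SAP*

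**What the plan says.** **The question.** Section 5, Aim 1 asks whether neurocognitive and functional outcomes "are better when CT is coupled with tDCS, an intervention that will increase neuroplasticity and augment training effects". H1.2 puts the same question on the primary outcome, the NIH Toolbox Fluid Cognition Composite: tDCS combined with CT against sham.

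**Phase 1.** Section 6.1: "An initial cohort of 80 participants collected across the two sites will be assigned to one of four conditions". Half receive CT and half TC. Section 6.4 describes TC as educational videos with questions on their content, on the same schedule as CT and paired with stimulation in the same way. Section 6.2, on blocks of eight: "In phase 1, each block will have two participants for each arm".

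**The interim rule.** Once the 80 have completed 12-month follow-up, the interim asks whether CT is significantly better than TC. If it is, TC is dropped. The only other branch is: "If CT and TC are equally effective, groups will be collapsed at initiation of Phase 2 for planned assessment of adjunctive tDCS effects". No endpoint, significance level, equivalence margin or model term for training type accompanies the rule.

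**Phase 2 and the final set.** Section 6.1 continues: "In Phase 2, the remaining 280 participants will be randomized to the two CT arms (i.e., eliminating the TC arms"). It then describes the final tDCS analysis as covering participants in the CT arms, Phase 1 included, with a total of 360. The note under the Study Timeline in Section 6.3 says of the Phase 2 cohort: "The allocation ratio for the last cohort depends on results from IA".

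**The concern.** TC with tDCS is tDCS coupled with watching videos and answering questions about them. It is not the combination named in Aim 1 and H1.2. If TC participants enter the primary tDCS comparison, the trial estimates something other than what it says it will estimate.

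The condition for collapsing does not protect against this. Equal mean outcomes under CT and TC would say nothing about whether tDCS acts equally on both. Pooling needs the absence of a training-by-tDCS interaction, and the interim looks only at the difference between trainings. The protocol's own rationale makes an interaction plausible: Section 6.2.1 treats CT as the engine of change whose effects tDCS is meant to augment.

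At stake are the meaning of the primary estimate, possibly its size, and whether the analysis set is fixed in advance. The last is unclear even if the collapse branch never occurs, because the stated total does not fit the arms it is said to describe.

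**Working it through.** **1. Head count (inputs from Section 6.1).** Phase 1: 80 / 2 = 40 CT and 40 TC. Phase 2: 280.
- All participants: 40 + 40 + 280 = 360, which reproduces the plan's total.
- CT arms only: 40 + 280 = 320.

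The figure given for the CT arms therefore counts the 40 TC participants.

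**2. Balance (Section 6.2).** 80 / 8 = 10 blocks with two participants per arm in each, so about 20 per arm. The 40 TC participants are about 20 tDCS and 20 sham.

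**3. What pooling estimates.** If all 280 Phase 2 participants go to CT and the model has no training term:

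pooled effect = (320/360) × effect on CT + (40/360) × effect on TC = 0.889 × effect on CT + 0.111 × effect on TC.

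Writing r for the effect on TC divided by the effect on CT, the CT effect is multiplied by (320 + 40r)/360.

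**4. Power.** The documents give no SD, significance level, attrition rate or tDCS effect size for this comparison, so the following are assumptions: SD 1, two-sided 5% t-test, no dropout, true tDCS effect on CT of 0.3 SD. The standard error is √(2/n): 0.1118 at 160 per arm and 0.1054 at 180 per arm.

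| Analysis | Effect (SD) | Power |
|---|---|---|
| CT only, 160 vs 160 | 0.300 | 76% |
| Pooled, 180 vs 180, r = 0 | 0.267 | 71% |
| Pooled, r = 0.5 | 0.283 | 76% |
| Pooled, r = 1 | 0.300 | 81% |

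At r = 0 the z-statistic is multiplied by 0.889 × 0.1118/0.1054 = 0.94. Pooling breaks even when (320 + 40r)/360 × 0.1118/0.1054 = 1, that is at r of about 0.49.

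**5. What the interim can show about CT and TC.** At 40 vs 40 the 95% confidence interval has half-width 1.96 × √(2/40) = 0.44 SD. The chance of a non-significant result (same assumptions) is:

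| True CT–TC difference (SD) | Chance of non-significance |
|---|---|
| 0.2 | 86% |
| 0.3 | 74% |
| 0.5 | 40% |
| 1.0 | 1% |

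The first three differences are illustrative. The last is the level that Section 4.3.3 says CT effects generally exceed immediately after training.

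**6. What Phase 1 could show about the interaction.** With 20 per cell the standard error of the training-by-tDCS interaction is √(4/20) = 0.447 SD. For 80% power it would have to be about (1.96 + 0.84) × 0.447 = 1.25 SD. At 0.3 SD, power is about 10%. Phase 1 could not support the pooling assumption even if the interaction were tested.

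**The case against.** **The collapse branch may never arise.** The protocol expects CT to win. H1.1 assesses CT against control at the end of Phase 1 on the trained BrainHQ tasks, where a large effect is most plausible, and at 1.0 SD a non-significant result has a chance of about 1%. This stands for the branch. It does not remove the 360, which is given without condition.

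**Non-significance is not the stated trigger.** A reader might infer that any non-significant interim leads to pooling. The text does not say so; it leaves equal effectiveness undefined. The documented gap is a missing criterion, and the table in step 5 shows only that non-significance would be a poor one.

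**Pooling does not bias the tDCS test.** A reader might infer that the comparators are mixed or that tDCS becomes confounded with training type. The blocks place TC participants about equally in both stimulation arms, so this is not supported. TC participants also answered content questions and were allocated to stimulation or sham, so they did more than watch videos.

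**Pooling may help.** A loss of power is not established. It follows only if tDCS has less than about half its CT effect on TC. Sections 4.3.5 and 6.2.1 cite effects of frontal tDCS on attention and working memory, and Section 6.1 plans to study tDCS individually as well as in combination. An average effect over both trainings is a legitimate target, but it is not the one in Aim 1 or H1.2.

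**The allocation statements may not conflict.** The sentence on the 280 directly follows the branch in which TC is dropped and may describe only that branch. The timeline note would then be consistent with it, and the 11% share and 0.89 factor would not apply to the collapse branch. Figure 2, which shows the arms, was not in the text available for this review. The wording needs reconciling; an outright contradiction is not shown.

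**Conclusion.** The point holds as a mismatch between the stated question and the analysis set. Following the collapse rule, or taking 360 as the final tDCS sample, brings 40 TC participants (11% of 360) into a comparison defined as tDCS added to CT. That changes the estimand to an average over two trainings.

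The numerical consequence is modest. The effect is multiplied by 0.89 if tDCS does nothing on TC, and power at an assumed 0.3 SD lies between 71% and 81%, against 76% with CT only. These figures rest on all 280 Phase 2 participants going to CT, SD 1, a two-sided 5% test, no dropout, and a tDCS effect on TC between zero and its effect on CT. The head count, 320 against 360, rests on the documents alone.

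The interim cannot justify pooling. It addresses the training main effect, while the relevant interaction is untested and, at 20 per cell, practically untestable.

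**What to change.** 1. Define the primary tDCS comparison as CT+tDCS versus CT+sham in all participants randomised to CT in either phase, whatever the interim shows, and remove the collapse rule from that analysis.
2. Correct the planned number for that analysis from 360 to 320; keep 360 as the total randomised.
3. Report TC+tDCS versus TC+sham separately, or give a pooled analysis with training and training-by-tDCS terms as supportive.
4. Reconcile the Section 6.1 sentence on the 280 with the Section 6.3 timeline note, stating whether the Phase 2 arms and ratio depend on the interim.

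If the sponsor prefers to keep pooling as primary, H1.2 has to be restated as the tDCS effect averaged over training type, with an endpoint and equivalence margin specified for the interim.

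**Cost.** Wording only. Up to 40 TC participants leave the primary comparison. That loses a little power if tDCS on TC has more than about half its effect on CT: at most about 5 points in the example above (81% to 76%), when the effects are equal.
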